#### 6.3.3. Confounders and effect modifiers

#### 6.3.3.1. Confounders

The following baseline characteristics will be evaluated as potential confounders:

- Demographic characteristics at index
  - Age (years, as well as categorized as 18-50, 50-64, 65+)
  - Sex (male, female)
  - Race (African American/Black, Asian, White, other race, unknown)
  - Ethnicity (Hispanic, non-Hispanic)
  - Marital status (Single, married/domestic partner, widowed, separated/divorced, unknown)
  - Geographic region (Northeast, Midwest, South, West, US Territories)
  - Risk of HIV transmission (MSM, PWID, Heterosexual, Vertical, Other)
  - Payer type (Medicaid, Medicare, Commercial insurance, AIDS Drug Assistance Programs (ADAP)/Ryan White, Cash)
- Clinical characteristics at index
  - Years since HIV diagnosis
  - Years since ART initiation
  - AIDS diagnosis at baseline

- Years since first OPERA visit
- Veterans Aging Cohort Study (VACS) Mortality Index score
- Weight (kg)
- $\circ \quad BMI (<30 \text{ vs.} \ge 30 \text{ kg/m}^2)$
- Co-infections
  - Hepatitis B co-infection
  - Hepatitis C co-infection
  - Syphilis infection (ever)
- o Comorbidities
  - Autoimmune disease
  - Cardiovascular disease
  - Invasive cancer
  - Endocrine disorder
  - Mental health disorder
  - Liver disease
  - Bone disorder
  - Peripheral neuropathy
  - Renal disease
  - Hypertension
  - Substance abuse
  - Any of the above
- Concomitant Medications
  - Anticonvulsants
    - Carbamazepine
    - Oxcarbazepine
    - Phenobarbital
    - Phenytoin
  - Antimycobacterials
    - Rifampin
    - Rifapentine
    - Rifabutin
  - Glucocorticoids
    - Dexamethasone
  - Macrolide or ketolide antibiotics
    - Azithromycin
    - Clarithromycin
    - Erythromycin
  - Narcotic analgesic
    - Methadone
- ART regimens prior to CAB+RPV LA
  - Number of core agents experienced
  - o Number of ARV classes experienced
  - Duration of last ARV regimen
  - o Prior core agent class
- Baseline virologic characteristics
  - o HIV viral load
    - Test result available (yes/no)
    - Continuous (copies/mL and log10 copies/mL)

- Categorical
  - o <50 copies/mL
  - $\circ$   $\geq$ 50 to  $\leq$ 200 copies/mL
  - $\circ \geq 200 \text{ to } < 1,000 \text{ copies/mL}$
  - $\circ \ge 1,000 \text{ to} < 10,000 \text{ copies/mL}$
  - $\circ \ge 10,000 \text{ to } < 100,000 \text{ copies/mL}$
  - $0 \ge 100,000 \text{ copies/mL}$
  - Missing
- Baseline immunologic characteristics
  - o CD4 cell count
    - Test result available (yes/no)
    - Continuous (cells/µL)
    - Categorical
      - $\circ$  >500 cells/ $\mu$ L
      - $\circ$  >350 to  $\leq$ 500 cells/ $\mu$ L
      - $\circ$  >200 to  $\leq$ 350 cells/ $\mu$ L
      - $\circ$  >50 to  $\leq$ 200 cells/ $\mu$ L)
      - $\leq$ 50 cells/ $\mu$ L
      - Missing

#### 6.3.3.2. Effect modifiers

Participant characteristics, adherence, persistence, discontinuation and virologic effectiveness will be compared in subgroups stratified by viral load at initiation (<50 copies/mL vs. ≥50), BMI (≥30 kg/m² vs. <30 kg/m²), age (18-50, 50-64, ≥65 years), race/ethnicity (non-Hispanic Black, Hispanic, non-Hispanic White), and sex/race (non-Hispanic Black men, Hispanic men, Black women) strata at initiation of CAB+RPV LA.

#### 6.4. \*Data source

The OPERA® clinical cohort is a multi-site observational database built from the complete patient health records managed in EHR systems from more than 400 participating caregivers at 142 separate locations throughout the US (Figure 3). Through their membership in OPERA®, medical practices meet the Centers for Medicare & Medicaid Services (CMS) Merit-based Incentive Payment System (MIPS) Incentive Program for Integration with a Specialized Registry. OPERA®-participating physicians and ancillary healthcare providers have documented the care of over 1 million patients in their EHRs, including over 150,000 PWH of which approximately 20% are women, representing 13% of all the PWH linked to care in the US. The OPERA® database is refreshed from these EHR systems at each clinic daily providing up-to-date data for both clinicians and researchers. In total, there are more than 13 million documented prospective visits in the EHR systems for PWH and 4.5 million prescriptions written for ART medications. The average years of follow-up (years of documenting patient visits prospectively in the EHR) for PWH in OPERA® is 5.6 years and there are over 30,000 PWH who have ten years or more of follow-up.

Figure 1. United States Map of OPERA® HIV+ Population and Centers for

Disease Control (CDC) State-by-State Estimates (2017)

## 6.5. \*Study size

Over two years (21JAN2021 and 28FEB2023), there were 1,843 individuals who were 18 years of age or older with HIV-1 in OPERA who were active in care and had received their first CAB+RPV injection. Of these, 1,578 had viral loads <50 copies/mL at first injection, and 229 had viral loads ≥50 copies/mL (36 had no viral load data available at first injection). Study size is expected to grow for Year 3, Year 4, and Year 5 making these calculations underestimates.

Confidence intervals, constructed using the asymptotic (Wald) method based on a normal approximation, are presented in Table 1, and are designed to give estimates of precision for a variety of sample sizes and event probabilities.

The example sample sizes in Table 1 reflect the overall sample size as well as the strata based on viral load at first CAB+RPV LA injection.

**Table 1. Confidence Intervals for Proportions** 

Confidence Level	Sample Size	CI Width	Event Proportion	Lower Limit	Upper Limit
0.95	1843	0.01	0.01	0.01	0.01
0.95	1843	0.02	0.05	0.04	0.06
0.95	1843	0.03	0.1	0.09	0.11
0.95	1843	0.04	0.2	0.18	0.22

Protocol Final 216990 – Amendment 2

		216990 – Amendment 2			
Confidence Level	Sample Size	CI Width	Event Proportion	Lower Limit	Upper Limit
0.95	1843	0.04	0.3	0.28	0.32
0.95	1843	0.04	0.4	0.38	0.42
0.95	1843	0.05	0.5	0.48	0.52
0.95	1843	0.04	0.6	0.58	0.62
0.95	1843	0.04	0.7	0.68	0.72
0.95	1843	0.04	0.8	0.78	0.82
0.95	1843	0.03	0.9	0.89	0.91
0.95	1578	0.01	0.01	0.01	0.01
0.95	1578	0.02	0.05	0.04	0.06
0.95	1578	0.03	0.1	0.09	0.11
0.95	1578	0.04	0.2	0.18	0.22
0.95	1578	0.05	0.3	0.28	0.32
0.95	1578	0.05	0.4	0.38	0.42
0.95	1578	0.05	0.5	0.48	0.52
0.95	1578	0.05	0.6	0.58	0.62
0.95	1578	0.05	0.7	0.68	0.72
0.95	1578	0.04	0.8	0.78	0.82
0.95	1578	0.03	0.9	0.89	0.91
0.95	136	0.03	0.01	-0.01	0.03
0.95	136	0.07	0.05	0.01	0.09
0.95	136	0.10	0.1	0.05	0.15
0.95	136	0.13	0.2	0.13	0.27
0.95	136	0.15	0.3	0.22	0.38
0.95	136	0.16	0.4	0.32	0.48
0.95	136	0.17	0.5	0.42	0.58
0.95	136	0.16	0.6	0.52	0.68
0.95	136	0.15	0.7	0.62	0.78
0.95	136	0.13	0.8	0.73	0.87
0.95	136	0.10	0.9	0.85	0.95
0.95	93	0.04	0.01	-0.01	0.03
0.95	93	0.09	0.05	0.01	0.09
0.95	93	0.12	0.1	0.04	0.16
0.95	93	0.16	0.2	0.12	0.28
0.95	93	0.19	0.3	0.21	0.39
0.95	93	0.20	0.4	0.30	0.50
0.95	93	0.20	0.5	0.40	0.60
0.95	93	0.20	0.6	0.50	0.70
0.95	93	0.19	0.7	0.61	0.79
0.95	93	0.16	0.8	0.72	0.88
0.95	93	0.12	0.9	0.84	0.96

CI, confidence interval

This study will measure numerous health outcomes. CI widths are widest for proportions of 50%. Based on an overall sample size of 1843, the study will allow for estimation of parameters with a maximum CI width of 0.05. Based on strata sizes of 1578, 136, and 93, the study will allow for estimation of parameters with maximum CI widths of 0.05, 0.17 and 0.20, respectively.

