#### Proposed changes in study objectives:

The proposed changes to the study objectives are:

- 1. Primary objective:
  - a. Factors associated with confirmed virologic failure was not listed as a separate primary objective in the initial study but was assessed as part of virologic effectiveness analysis. It is called out as a separate primary objective in this study as we will enough numbers to conduct this analysis.
- 2. Secondary objective:
  - a. Sub-group analyses by viral load (<50 copies/mL, 50 <200 copies/mL, and ≥200 copies/mL), BMI (<30 and ≥30 kg/m²) and age (<18, 18-50, 50-64, ≥65 years) at initiation to assess characteristics, adherence, persistence, discontinuation and virologic effectiveness are explicitly called out as a secondary objective in this study. Some of the sub-groups listed were evaluated in the initial study but was not listed as a study objective.
- 3. Oral lead-in and oral bridging explored in the initial study will not be assessed in this study as these events cannot be reliably observed in the OPERA data.

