## 6.3.2.6. Virologic effectiveness

Among suppressed (VL< 50 copies/mL) at initiation:

Maintaining virologic suppression: Among PWH who were suppressed (VL <50 copies/mL) at baseline, the number and proportion who remain suppressed (VL <50 copies/mL) throughout all of follow-up will be reported, as well as the number and proportion who are suppressed (VL <50 copies/mL) at last follow-up. Proportion of individuals with VL <50 copies/mL during the first 6 months, and at 6, 12, 24, 36, 48, and 60 months following initiation of CAB+RPV LA regimen will be described.

Confirmed virologic failure: Confirmed virologic failure will be defined as 2 consecutive follow-up VLs ≥200 copies/mL OR 1 follow-up VL ≥200 copies/mL + discontinuation within 4 months of VL ≥200 copies/mL. The number and proportion of PWH with confirmed virologic failure will be reported as well as the time to virologic failure (months). Proportion of individuals with confirmed virologic failure (CVF) during the first 6 months, and at 6, 12, 24, 36, 48 and 60 months following initiation of CAB+RPV LA regimen will be described.

Among viremic ( $VL \ge 50$  copies/mL) at initiation:

Achieving virologic suppression: Among PWH who were viremic ( $VL \ge 50$  copies/mL) at baseline, the number and proportion who achieve a VL < 50 copies/mL at any point during follow-up will be reported, as well as the number and proportion who achieve a VL < 50 copies/mL at last follow-up. Proportion of individuals with VL < 50 copies/mL during the first 6 months, and at 6, 12, 24, 36, 48 and 60 months following initiation of CAB+RPV LA regimen will be described.

Non-response: VL ≥50 copies/mL after 6 and 12 months following initiation of CAB+RPV LA regimen and also no VL of <50 copies/mL during follow up will be described.

Confirmed virologic failure defined as:

- Suppressed to <50 copies/mL followed by either 2 VLs ≥200 copies/mL or
  1 VL ≥200 copies/mL and discontinuation within 4 months for every other month
  regimen; and discontinuation within 2 months for monthly regimen. Proportion of
  individuals with confirmed virologic failure (CVF) during the first 6 months, and at
  6, 12, 24, 36, 48 and 60 months following initiation of CAB+RPV LA regimen will
  be described.

- FDA's ask: Suppressed to <50 copies/mL followed by either 2 VLs ≥400 copies/mL

Protocol Final ViiV Healthcare 216990 - Amendment 2

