# 6.7. \*Data analysis

# 6.7.1. Primary Analysis

## 6.7.1.1. Main Analytical approach

Baseline characteristics and outcomes will be described using counts and absolute and relative frequencies for categorical variables and medians with interquartile ranges (IQR) for continuous variables. For outcomes assessed at any point during follow-up, incidence rates will be estimated using unadjusted Poisson regression, accounting for person-time since index (i.e., first CAB+RPV LA injection).

Analyses will be stratified by viral load (<50 copies/mL vs. ≥50 copies/mL), BMI (<30 kg/m² vs. ≥30 kg/m²), age (18-50, 50-64, ≥65 years), race/ethnicity (non-Hispanic Black, Hispanic, non-Hispanic White), and sex/race (non-Hispanic Black men, Hispanic men, Black women) strata at first CAB+RPV LA injections as sample size allows to assess characteristics, adherence, persistence, discontinuation and virologic effectiveness. Other demographic and clinical variables may also be considered for stratification, if relevant.

Factors including age, sex, race, geographic region, BMI, IDU, CD4 count, any comorbidities associated with confirmed virologic failure will be assessed using multiple logistic regression.

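### Section 6.5 states precision for viral-load strata of 136 and 93 that the current plan does not analyse, and its remark on cohort growth does not hold for the last reachable time point at each data cut

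*Protocol*

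**What the plan says.** Protocol section 6.5 reports, for the period to 28FEB2023, that "there were 1,843 individuals who were 18 years of age or older with HIV-1 in OPERA who were active in care", each with a first injection on record. Of these, "1,578 had viral loads <50 copies/mL at first injection, and 229 had viral loads ≥50 copies/mL"; a further 36 had no viral load. The section adds that "The example sample sizes in Table 1 reflect the overall sample size as well as the strata based on viral load" at first injection, that the intervals are "constructed using the asymptotic (Wald) method based on a normal approximation", and that growth of the cohort in Years 3 to 5 makes the calculations underestimates.

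Table 1 then gives rows for n = 1,843, 1,578, 136 and 93. The closing text gives a maximum width of 0.05 for 1,843 and continues: "Based on strata sizes of 1578, 136, and 93, the study will allow for estimation of parameters with maximum CI widths"; the three values given are 0.05, 0.17 and 0.20.

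Section 6.7.1.1 sets the analysis strata: "Analyses will be stratified by viral load (<50 copies/mL vs. ≥50 copies/mL"). The secondary objectives and section 6.3.3.2 use the same two groups.

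Section 6.3.2.6 plans virologic proportions during the first 6 months "and at 6, 12, 24, 36, 48, and 60 months following initiation of CAB+RPV LA regimen". Section 6.2 starts eligibility on 21JAN2021 for every cut and ends observation on 29FEB2024, 28FEB2025 and 28FEB2026.

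**The concern.** Section 6.5 is the protocol's only justification of study size, and it disagrees with itself. The text describes one viremic stratum of 229. The table and its summary give precision for 136 and 93, which are not strata of the current plan. A reader who wants the precision for the viremic group finds two figures, and neither applies.

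Two further features bear on how Table 1 is read. It prints a negative lower limit for a proportion in two rows, which raises the question of how well the method serves rare outcomes such as confirmed virologic failure. And the statement that growth makes the calculations underestimates is general, although follow-up of 36, 48 or 60 months depends on when a person started, not only on how many eventually start.

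**Working it through.** **1. Reproduce the plan's figures.** Wald limits are p ± 1.96·√(p(1−p)/n), and the width is greatest at p = 0.5, where it equals 1.96/√n.

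| n | Maximum width | Stated |
|---|---|---|
| 1,843 | 0.0457 | 0.05 |
| 1,578 | 0.0493 | 0.05 |
| 136 | 0.1681 | 0.17 |
| 93 | 0.2032 | 0.20 |

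All 44 rows of Table 1 reproduce to two decimals for their printed n. The arithmetic is right; the stratum sizes are not those of the current plan.

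**2. Compare the strata.** 1,578 + 229 + 36 = 1,843, so the counts in the text are complete. 136 + 93 = 229, so the two small sizes are a split of the viremic group. The summary of Amendment 1 lists a former three-way grouping, "50 <200 copies/mL, and ≥200 copies/mL" being its upper two classes, and Amendment 2 merged them. That this is where 136 and 93 come from is an inference, since Table 1 does not label them. The amendment summary serves only to explain the numbers; the inconsistency lies within the current text.

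**3. The missing row.** At n = 229 the maximum width is 1.96/√229 = 0.1295, or 0.13 (limits 0.435 to 0.565).

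**4. Wald limits at a 1% proportion.** Coverage is by exact binomial summation at a true proportion of 1%.

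| n | Wald limits | Wilson limits | Wald coverage |
|---|---|---|---|
| 1,843 | 0.0055 to 0.0145 | 0.0064 to 0.0157 | about 94% |
| 1,578 | 0.0051 to 0.0149 | 0.0061 to 0.0162 | about 94% |
| 229 | -0.003 to 0.023 | 0.003 to 0.033 | about 90% |

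At n = 229 the chance of no events is 0.99^229 = 0.10, and the Wald interval then has zero width. At the two large sizes the printed 0.01 to 0.01 is two-decimal rounding of usable limits.

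**5. Who can reach the last time point.** Counting back 36 months from 29FEB2024, 48 months from 28FEB2025 and 60 months from 28FEB2026 gives 28FEB2021 each time. Only people indexed from 21JAN2021 to 28FEB2021 qualify, an entry window of 11 + 28 = 39 days. The observation windows last 37.3, 49.2 and 61.2 months, so 48 and 60 months cannot be reached at Year 3, nor 60 months at Year 4.

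**6. Illustrative precision there.** The protocol gives no accrual by date. Assumption: uniform accrual of the 1,843 over 21JAN2021 to 28FEB2023, which is 769 days. Then 1,843/769 = 2.40 per day, and 39 days give about 93 people before discontinuation, loss to follow-up or a missing viral load.

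| Scenario | n | Maximum width |
|---|---|---|
| Uniform accrual, all remain | 93 | 0.20 |
| Half remain | 47 | 0.29 |
| Twice that accrual, all remain | 187 | 0.14 |

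This 93 matches the stratum size in Table 1 only by coincidence.

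**The case against.** The strongest reply is that little depends on Table 1. The study is descriptive and takes every eligible person in the database, the sizes are called examples, and the figure that should replace 0.17 and 0.20 is more favourable than both. All of that stands. It limits the weight of the point but does not reconcile the text with the table, because the same section says the example sizes are the viral-load strata.

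Several stronger readings are tempting, and the documents do not support them.

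- **Table 1 is invalid for rare outcomes in general.** At 1,843 and 1,578 Wald coverage at 1% is about 94%. Much worse coverage can be computed at 1% for n = 93 and n = 136 (about 61% and 74%), but those are the rows that should go. The protocol gives no expected failure rate; 1% is one of the table's example proportions.
- **The study will report Wald intervals.** The method is stated for Table 1 only. Section 6.7.1.1 names no interval method for the results, and that choice may properly sit in a statistical analysis plan.
- **The protocol promises a width of 0.05 at 60 months.** It ties 0.05 to n = 1,843 and states no precision for any late time point. What fails is the general remark that growth makes the calculations underestimates.
- **At most 93 people can reach the last time point.** That figure rests on assumed uniform accrual and is not a bound. Only the 39-day window follows from the dates, and any visit window around the nominal month, which is not defined, could change it.
- **All late time points are thin.** The limit concerns the last reachable point at each cut. At Year 5, for example, 36 months is open to anyone indexed by 28FEB2023, which covers the whole base of 1,843 before attrition.

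Restricting which time points are given prominence would be a preference, since the protocol designates none as a headline.

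**Conclusion.** The point holds as an inconsistency in section 6.5 that is cheap to correct. The stated maximum widths of 0.17 and 0.20 do not belong to any stratum of the current plan; the right figure for the viremic stratum is 0.13 at n = 229. This rests only on the protocol's own counts, and the error is conservative.

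The weakness of the Wald limits is confined to rare proportions in the small stratum: a slightly negative lower limit and coverage of about 90% at 1% and n = 229.

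The time-point limit follows from the study dates alone. Later starters cannot add to a closed 39-day entry window, so the underestimates remark is wrong for 36 months at Year 3, 48 at Year 4 and 60 at Year 5, and three combinations of cut and time point cannot be reached at all. How wide the intervals will be there is not documented. Under the accrual scenarios shown, the maximum width is roughly 0.14 to 0.29.

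**What to change.** In section 6.5:

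1. Replace the rows for 136 and 93 with rows for n = 229, and rewrite the closing sentence to give maximum widths of 0.05 (n = 1,578) and 0.13 (n = 229).
2. Print Table 1 with Wilson or exact limits to three decimals. This removes the negative limits and the uninformative 0.01 to 0.01 rows. Changing the stratum size alone would not, because the Wald limit at n = 229 and 1% is still below zero.
3. Qualify the underestimates sentence: add the precision expected at the last reachable time point for each data cut, with the accrual assumption stated or actual counts of people indexed by 28FEB2021 in its place.
4. Mark 48 and 60 months at Year 3, and 60 months at Year 4, as not estimable at that cut.

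The cost is one revised table and a few sentences, with no change to design, population or data collection. The downside is that the stated precision for the latest time points becomes less favourable.

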## 6.6. \*Data management

## 6.6.1. Data handling conventions

The data used in this research study will be deidentified data and research staff will not have access to personally identifiable information. All data are managed according to regulations such as the Health Insurance Portability and Accountability Act (HIPAA) and the Health Information Technology for Economic and Clinical Health (HITECH) Act. These regulations and guidelines expand upon the ethical principles detailed in the 1964 Declaration of Helsinki. Epividian will own the data and be responsible for data integrity and privacy. ViiV Healthcare will not have access to individual patient-level data (including personally identifiable information).

#### 6.6.2. Resourcing needs

Not applicable.

## 6.6.3. Timings of Assessment during follow-up

Year 3	
Observation	21JAN2021 through 29FEB2024
Analysis	2Q2024
Year 4	
Observation	21JAN2021 through 28FEB2025
Analysis	2Q2025
Year 5	
Observation	21JAN2021 through 28FEB2026
Analysis	3Q2026

# 6.7. \*Data analysis

# 6.7.1. Primary Analysis

## 6.7.1.1. Main Analytical approach

Baseline characteristics and outcomes will be described using counts and absolute and relative frequencies for categorical variables and medians with interquartile ranges (IQR) for continuous variables. For outcomes assessed at any point during follow-up, incidence rates will be estimated using unadjusted Poisson regression, accounting for person-time since index (i.e., first CAB+RPV LA injection).

Analyses will be stratified by viral load (<50 copies/mL vs. ≥50 copies/mL), BMI (<30 kg/m² vs. ≥30 kg/m²), age (18-50, 50-64, ≥65 years), race/ethnicity (non-Hispanic Black, Hispanic, non-Hispanic White), and sex/race (non-Hispanic Black men, Hispanic men, Black women) strata at first CAB+RPV LA injections as sample size allows to assess characteristics, adherence, persistence, discontinuation and virologic effectiveness. Other demographic and clinical variables may also be considered for stratification, if relevant.

Factors including age, sex, race, geographic region, BMI, IDU, CD4 count, any comorbidities associated with confirmed virologic failure will be assessed using multiple logistic regression.

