#### \*Data analysis

Baseline characteristics and outcomes will be described using counts and relative frequencies for categorical variables and medians with interquartile ranges (IQR) for continuous variables. For outcomes assessed at any point during follow-up, incidence rates will be estimated using unadjusted Poisson regression, accounting for person-time since index (i.e., first CAB+RPV LA injection). Analyses will be stratified by viral load (<50 copies/mL vs. ≥50 copies/mL), BMI (<30 kg/m2 vs. ≥30 kg/m2), age (18-50, 50-64, ≥65 years), race/ethnicity (non-Hispanic Black, Hispanic, non-Hispanic White), and sex/race (non-Hispanic Black men, Hispanic men, Black women) strata at initiation of CAB+RPV regimen. Factors associated with confirmed virologic failure will be assessed using multiple logistic regression.

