#### **Secondary Objectives:**

- 1. Sub-group analyses by viral load (VL <50, ≥50copies/mL) at initiation, BMI (<30 and ≥30 kg/m²) at initiation and age (18-50, 50-64, ≥65 years) at initiation to assess characteristics, adherence, persistence, discontinuation and virologic effectiveness
- 2. To estimate the frequency of documented injection site reactions and hypersensitivity reactions among PWH receiving CAB+RPV LA injections at Year 3, Year 4, and Year 5 of availability
- 3. To compare baseline characteristics and treatment outcomes (persistence/discontinuation, adherence, maintaining virologic suppression, confirmed virologic failure) between oral ART and CAB+RPV LA use in PWH at Year 4 and Year 5 of availability
- 4. To describe baseline characteristics and treatment outcomes (persistence/discontinuation, adherence, virologic effectiveness) among PWH receiving CAB+RPV LA injections at Year 4 and Year 5, in subgroups of interest
  - a. Race/ethnicity (Non-Hispanic Black, Hispanic, Non-Hispanic White)
  - b. Sex/race (Non-Hispanic Black men, Hispanic men, Black women)
- 5. Among individuals with confirmed virologic failure (CVF): to describe HIV resistance and proviral testing at the time of CVF, as well as history of resistance and proviral DNA testing prior to CVF at Year 4 and Year 5 of availability

ViiV Healthcare Protocol Final 216990 – Amendment 2

- 6. Among individuals with confirmed virologic failure (CVF): to describe the ART regimens after CVF in OPERA at Year 4 and Year 5 of availability
  - a. To describe the baseline characteristics (demographic, clinical, treatment patterns) of ART regimen after CVF
  - b. To describe virologic response (suppression, non-response, confirmed virologic failure) to ART regimen after CVF

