## **Study Period:**

- o Year 3:
  - Period of eligibility: 21JAN2021-31DEC2023
  - Period of observation: 21JAN2021-29FEB2024
- O Year 4:
  - Period of eligibility: 21JAN2021-31DEC2024
  - Period of observation: 21JAN2021-28FEB2025
- o Year 5:
  - Period of eligibility: 21JAN2021-31DEC2025
  - Period of observation: 21JAN2021-28FEB2026

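### The single unadjusted Poisson rate can shift between data cuts and subgroups through follow-up mix alone; discontinuation, which has no fixed-time summary, is the most exposed

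*Protocol*

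**What the plan says.** Section 6.7.1.1 (Main Analytical approach) states, for outcomes assessed at any point in follow-up: "incidence rates will be estimated using unadjusted Poisson regression, accounting for person-time since index (i.e., first CAB+RPV LA injection"). The Data analysis paragraph of the synopsis repeats this: "incidence rates will be estimated using unadjusted Poisson regression, accounting for person-time since index". Neither names a term or interval for time on regimen, and section 6.7.1.2 plans no sensitivity analysis.

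The cuts are cumulative from one start date. Year 3 has "Period of eligibility: 21JAN2021-31DEC2023" and "Period of observation: 21JAN2021-29FEB2024"; Year 4 has "Period of observation: 21JAN2021-28FEB2025"; Year 5 has "Period of eligibility: 21JAN2021-31DEC2025", observed to 28 February 2026. Primary objectives are reported at each cut, and section 6.3.3.2 says that discontinuation and virologic effectiveness, among others, will be compared across subgroups.

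The fixed-time summaries differ by outcome:

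- Section 6.3.2.6 (Virologic effectiveness) gives suppression and confirmed virologic failure (CVF) in the first 6 months and at 6, 12, 24, 36, 48 and 60 months. For those suppressed at initiation it also gives time to failure.
- Section 6.3.2.3 (Persistence) gives only time on regimen and the number and proportion still on it at study end.
- Section 6.3.2.4 defines discontinuation as more than 67 days (monthly dosing) or 127 days (every-other-month dosing) after the last injection.

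**The concern.** Events divided by person-time summarise risk in one number that does not depend on length of follow-up only if the hazard is constant. Otherwise the number depends on how much early and late person-time a group contributes. Entry stays open until about two months before each cut while the longest follow-up grows by a year, so that mix changes by design. It also differs between subgroups that started at different calendar times or leave at different rates.

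The protocol's own definitions make a constant hazard doubtful. If discontinuation is dated when the permitted gap is exceeded (the protocol does not state the dating), it cannot occur in the first 67 or 127 days after index. In people viremic at initiation, CVF requires suppression first, so some early person-time carries no risk of it.

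At stake is interpretation. Rates from three cuts, or from several subgroups, will stand side by side. A difference produced by follow-up mix could be taken for a difference in how the regimen performs.

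**Working it through.** **The plan's own figures.** No incidence rate or precision for a rate is stated. Table 1 concerns proportions; its maximum width at N = 1843 reproduces (2 × 1.96 × √(0.25/1843) = 0.0457, stated as 0.05). It does not bear on this point.

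**Inputs from the protocol (Study Period).** Administrative follow-up runs from last eligible entry to cut (shortest) and from 21 January 2021 to cut (longest):

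| Cut | Shortest | Longest |
|---|---|---|
| Year 3 | 60 days | 1134 days = 3.10 years |
| Year 4 | 59 days | 1499 days = 4.10 years |
| Year 5 | 59 days | 1864 days = 5.10 years |

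**Assumed, because the protocol does not give them.** Entry is uniform over each eligibility period, and the hazard since index is the same for everyone. For early risk, the late hazard is 1 per 100 person-years (PY), other exits are 10 per 100 PY, and the hazard is multiplied by HR in the first 6 or 12 months. For the lag, the hazard is zero up to 67 or 127 days and then 10 per 100 PY, with other exits at 2 per 100 PY.

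**Formula.** Expected rate = expected events / expected person-time. With a two-piece hazard this is

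rate = late hazard × [1 + (HR − 1) × s],

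where s is the share of person-time in the early window. Integrating over the follow-up ranges above gives, for HR = 2:

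| Early window | s, Year 3 | s, Year 4 | s, Year 5 |
|---|---|---|---|
| 6 months | 0.321 | 0.257 | 0.217 |
| 12 months | 0.573 | 0.469 | 0.401 |

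Example, HR = 2 over 12 months: 1 + 0.573 = 1.57 at Year 3 and 1 + 0.401 = 1.40 at Year 5, a ratio of 0.89.

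**Results per 100 PY, identical risk for everyone:**

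| Assumed hazard | Year 3 | Year 4 | Year 5 | Year 5 / Year 3 |
|---|---|---|---|---|
| Constant | 1.00 | 1.00 | 1.00 | 1.00 |
| 2× for 6 months | 1.32 | 1.26 | 1.22 | 0.92 |
| 2× for 12 months | 1.57 | 1.47 | 1.40 | 0.89 |
| 3× for 12 months | 2.15 | 1.94 | 1.80 | 0.84 |
| 5× for 12 months | 3.31 | 2.89 | 2.62 | 0.79 |
| No event before 67 days, then 10 | 8.76 | 9.01 | 9.17 | 1.05 |
| No event before 127 days, then 10 | 7.72 | 8.18 | 8.47 | 1.10 |

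At a discontinuation-like level (late hazard 8 per 100 PY, other exits 2), the ratios are nearly the same: 0.92 for 2× over 6 months and 0.80 for 5× over 12 months.

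**Two groups at the same cut.** At Year 5, compare a group whose entry rises linearly with one whose entry falls linearly, both with the same hazard. The rate ratio is 1.00 under constant hazard, 1.11 for 2× over 6 months and 1.23 for 3× over 12 months. With uniform entry but other exits of 40 versus 5 per 100 PY, it is 1.08 and 1.17 in the two non-constant scenarios.

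**After the change.** In the scenario of 3× over 12 months, rates split at 12 months are 3.00 and 1.00 per 100 PY at all three cuts, where the single rate gave 2.15, 1.94 and 1.80.

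**Scale against sampling error.** If N = 1578 (an assumption; it is the count suppressed at first injection in the Study size section), the same scenario yields about 49, 56 and 62 events. The relative 95% half-width is 1.96/√49 = 28% at Year 3 and 1.96/√62 = 25% at Year 5, against a shift of 16%.

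**The case against.** Several counter-arguments stand and limit the point.

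- **Scope.** Poisson rates apply only to any-point outcomes. Suppression and CVF also have proportions at 6 to 60 months that do not rest on the rate. It would be wrong to infer that every outcome is reduced to one constant rate.
- **Certainty and direction.** A reader might infer that rates will fall from Year 3 to Year 5. The documents do not support that: no hazard shape is given, constant hazard produces no change, and the discontinuation lag pushes the rate up.
- **Oral versus injectable.** Secondary objective 3 is "To compare baseline characteristics and treatment outcomes (persistence/discontinuation, adherence, maintaining virologic suppression, confirmed virologic failure) between oral ART and CAB+RPV LA use", but no method is attached to it. The index for the rate is described only as the first CAB+RPV LA injection. A confounded Poisson rate ratio between the two cohorts is therefore not something the protocol plans.
- **Trend across cuts.** No objective tests change from Year 3 to Year 5.
- **Size.** The shift computed above is smaller than the sampling error of one rate.
- **Remedy.** Spreading 49 to 62 events over six intervals leaves roughly 8 to 10 in each, too few in small subgroups.

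It can also be said that a crude rate is a legitimate descriptive average and that splitting person-time is a matter for the analysis plan. The first is true, which is why the rate can stay. The second carries less weight: the protocol itself fixes the unadjusted form, says that subgroups will be compared, and lists time points for virologic outcomes but none for discontinuation. The sampling-error argument is also partial, because the shift is systematic and does not shrink as the cohort grows.

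**Conclusion.** The point holds in limited form. For any-point outcomes, the planned rate can differ between cuts and between compared subgroups through follow-up mix alone, provided risk varies with time since index. Under the assumptions shown, the Year 3 to Year 5 change is about -8% to -21% for two- to five-fold early risk, about +5% to +10% under the 67- or 127-day lag, and zero under constant hazard. The lag figures also assume that discontinuation is dated when the gap is exceeded.

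The practical gap is discontinuation and persistence. This is a primary objective, and each of its planned summaries (time on regimen, proportion on regimen at study end, crude rate) depends on follow-up mix or can do so, with no fixed-time figure beside them. For suppression and CVF the existing proportions largely cover the need. The change is cheap and worth making; it does not invalidate the planned analysis.

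**What to change.** In sections 6.3.2.3, 6.3.2.4 and 6.7.1.1, and in the synopsis:

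1. Add cumulative incidence of discontinuation at the months already used for virologic outcomes (6, 12, 24, 36, 48 and 60), as far as each cut reaches, with numbers at risk. Alternatively, give rates in a few time-on-regimen intervals, for example 0-6, 6-12 and over 12 months. A few intervals are preferable to six, given the likely event counts.
2. State the date assigned to a discontinuation event (for example last injection, or the day the gap is exceeded), since this decides whether early person-time can contain events.
3. Keep the overall Poisson rate as a descriptive summary.
4. Base any comparison across cuts or subgroups on the time-specific figures, or on a model with time interval as a term. Do the same for oral versus injectable if rates are used there.

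The cost is some wording, extra table rows and wider interval-specific confidence intervals. The last month at each cut will be thin: the longest follow-up of 1134, 1499 and 1864 days exceeds 36, 48 and 60 months by only about 38 days (for example 1134 − 3 × 365.25 = 38), so only people who started in that first stretch can reach it.
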